8.3 Formulation of Test and Control Treatments

After induction of general anesthesia, the ECD will be connected to the Gaymar Medi-Therm III Hyper/Hypothermia Machine and tested for leaks according to the manufacturer's instructions. Then, it will be lubricated and placed into the esophagus of the subject in a manner identical to that of the standard OG tube used in LTx surgery.

The standard bladder temperature probe used in LTx operations will be connected to the PATIENT PROBE jack of the Gaymar Medi-Therm III, which will be used in AUTO/Rapid mode.

In both Study Arms (Mild Hypothermia and Normothermia), the subject will be given 2 grams of magnesium (Mg) sulfate IV at the beginning of surgery if the preoperative Mg < 2 mg/dL. This will be done because mild hypothermia may trigger a cold-induced diuresis and loss of electrolytes. Therefore, efforts will be made to keep the Mg normal (1.8-2.4 mg/dL) in both groups. Potassium will also be monitored carefully during surgery and replaced at the discretion of the attending anesthesiologist/study doctor.

Experimental treatment – Mild hypothermia (34-35 °C).

- Cooling will be initiated after induction of anesthesia and maintained throughout the anhepatic phase of LTx (Fig. 1). This will be done by selecting a Set Point temperature of 34.8 °C¹ on the Gaymar Medi-Therm III.
- In all feasible cases the surgeon will cover the peritoneal surface over the right kidney, which is exposed during the operation, with ice-cold sponges (lap sponges soaked in ice water and wrapped around ice cubes) to enhance cooling of the renal parenchyma. Local cooling will be applied to the right kidney beginning approximately 10 minutes prior to the anhepatic phase. The anhepatic phase is defined as application of the inferior vena cava (IVC) clamp and removal of the recipient liver.
- After the portal vein is reperfused, the ECD (by selecting a Set Point temperature of 37 °C on the Gaymar Medi-Therm III) and other standard measures (forced-air, fluid, and table warmers, plus a heated anesthesia circuit) will be used to actively re-warm the patient (expected warming rate ≥ 1 °C/hour). The goal is to achieve normothermia by case end.

Control – Normothermia (36.5-37.5 °C).

• After induction of anesthesia, the ECD (by selecting a Set Point temperature of 37 °C on the Gaymar Medi-Therm III) and standard warming measures will be used to maintain normothermia throughout the operation.

At the end of LTx surgery, the ECD will be removed from the patient prior to emergence from general anesthesia, extubation, and/or transport to the ICU.

¹ The original protocol used a set point of 34.4 °C. However, we found that the core temperature dropped significantly (~0.5 °C) during the anhepatic phase (due to the cold liver graft and ice pack on the right kidney). Thus, we have modified the Set Point temperature to 34.8 °C.

9 STUDY PROCEDURES AND GUIDELINES

A Schedule of Events representing the required testing procedures to be performed for the duration of the study is diagrammed in Appendix 1.

Prior to conducting any study-related activities, written informed consent and the Health Insurance Portability and Accountability Act (HIPAA) authorization must be signed and dated by the subject or subject's legal representative. If appropriate, assent must also be obtained prior to conducting any study-related activities.

9.1 Clinical Assessments

9.1.1 Concomitant Medications

All concomitant medication and concurrent therapies will be documented at Baseline/Screening. Dose, route, unit frequency of administration, and indication for administration and dates of medication will be captured.

9.1.2 Demographics

Demographic information (date of birth, gender, race) will be recorded at Screening.

9.1.3 Medical History

Relevant medical history, including history of current disease, other pertinent respiratory history, and information regarding underlying diseases will be recorded at Screening.

9.1.4 Physical Examination

A complete physical examination will be performed by either the investigator or a subinvestigator who is a physician at Screening (this is part of the standard anesthesia preoperative assessment prior to liver transplant surgery). New abnormal physical exam findings must be documented and will be followed by a physician or other qualified staff post-operatively.

9.1.5 Vital Signs

Body temperature, blood pressure, pulse, oximetry and respirations will be performed prior to induction of general anesthesia at Screening and continuously while receiving the Study Protocol in the OR during LTx.

9.1.6 Adverse Events

Information regarding occurrence of adverse events will be captured throughout the study. Duration (start and stop dates and times), severity/grade, outcome, treatment and relation to study drug will be recorded on the case report form (CRF).

9.2 Clinical Laboratory Measurements

9.2.1 Arterial Blood Gas

Arterial blood will be obtained and analyzed by point-of-care testing using an ABL-90 blood gas analyzer. This is standard of care during LTx at UCSF and no additional ABGs will be drawn outside of what is normally required for patient care.

9.3 Research Laboratory Measurements

9.3.1 Serum NGAL Measurements

At two time points, baseline (surgical incision) and 2 hours after reperfusion of the portal vein, blood will be collected for serum NGAL determination. At each blood draw, two serum separator tubes (gold top) will be filled. Each tube requires about 5 mL of blood, there will be 2 tubes collected per time point, and 2 time points, for a total of about 20 mL of blood (4 tubes).

After filling with blood, tubes will be inverted 5-times to mix clot activator with blood. Samples will sit undisturbed for 30 min to allow clot to form. Samples will be centrifuged at 1,000 x g for 15 minutes. Serum will be pipetted into Eppendorf tubes in 2 mL aliquots and frozen at \leq -20 °C until analysis, which will be performed *en batch*.

Serum NGAL determination will be performed using an enzyme-linked immunosorbent assay (ELISA) kit according to the manufacturer's instructions (R&D Systems, Inc.).

9.3.2 Urine NGAL Measurements

At two time points, baseline (surgical incision) and 2 hours after reperfusion of the portal vein, urine will be collected for NGAL determination. Approximately 10-15 mL of fresh urine will be aspirated from the Foley catheter collection chamber using a syringe, and dispensed into a 15-mL sterile tube (Falcon). The urine will be centrifuged at 1,000 x g for 15 min to pellet any solid material. The supernatant will be pipetted into Eppendorf tubes in 2 mL aliquots and frozen at \leq -20 °C until analysis, which will be performed *en batch*.

Urine NGAL determination will be performed using an ELISA kit according to the manufacturer's instructions (R&D Systems, Inc.).

10 EVALUATIONS BY VISIT

10.1 Visit 1 (Day 1, before and during LTx)

- 1. Review the study with the subject (subject's legal representative) and obtain written informed consent and HIPAA authorization and assent, if appropriate.
- 2. Assign the subject a unique screening number.
- 3. Record demographics data.
- 4. Record medical history, including a history of acute kidney injury, ascites, or hepatic encephalopathy, including diagnosis date, and prior treatments (dialysis, continuous renal replacement therapy (CRRT), large volume paracentesis).
- 5. Record concomitant medications.

- 6. Perform a complete physical examination.
- 7. Perform and record vital signs.
- 8. Perform and record oximetry.
- 9. Perform and record results of blood pressure testing.
- 10. Randomize subject (see Section 8.1).
- 11. Place ECD after induction of general anesthesia.
- 12. Implement intraoperative temperature protocol according to randomization (see Section 8.3).
- 13. Collect blood for ABGs (see Section 9.2) and NGAL determination (Section 9.3.1).
- 14. Collect urine for NGAL determination (see Section 9.3.2).
- 15. Remove ECD at the end of surgery.
- 10.2 Visit 2 (Follow-up prior to hospital discharge, window of 2 ± 1 weeks after LTx)
- 1. Record any Adverse Experiences.
- 2. Record changes to concomitant medications.
- 3. Perform complete physical examination.
- 4. Perform and record vital signs.
- 5. Perform and record oximetry.
- 6. If surrogate consent was obtained for the subject, and subject has now regained capacity, re-consent the patient for use of study data.

11 ADVERSE EXPERIENCE REPORTING AND DOCUMENTATION

11.1 Adverse Events

An adverse event (AE) is any untoward medical occurrence in a clinical investigation of a patient administered a treatment that does not necessarily have a causal relationship with the treatment. An AE is therefore any unfavorable and unintended sign (including an abnormal laboratory finding), symptom or disease temporally associated with the administration of an investigational treatment, whether or not related to that investigational treatment.

The Investigator will probe, via discussion with the subject, for the occurrence of AEs during each subject visit and record the information in the site's source documents. Adverse events will be recorded in the patient CRF. Adverse events will be described by duration (start and stop dates and times), severity, outcome, treatment and relation to study protocol, or if unrelated, the cause.

AE Severity

The National Cancer Institute's Common Terminology Criteria for Adverse Events (CTCAE) Version 3.0 should be used to assess and grade AE severity, including laboratory abnormalities judged to be clinically significant. The modified criteria can be found in the study manual. If the experience is not covered in the modified criteria, the

guidelines shown in Table 1 below should be used to grade severity. It should be pointed out that the term "severe" is a measure of intensity and that a severe AE is not necessarily serious.

Severity (Toxicity Grade)	Description
Mild (1)	Transient or mild discomfort; no limitation in activity; no medical
	intervention or therapy required. The subject may be aware of the sign
	or symptom but tolerates it reasonably well.
Moderate (2)	Mild to moderate limitation in activity, no or minimal medical
	intervention/therapy required.
Severe (3)	Marked limitation in activity, medical intervention/therapy required,
	hospitalizations possible.
Life-threatening (4)	The subject is at risk of death due to the adverse experience as it
	occurred. This does not refer to an experience that hypothetically
	might have caused death if it were more severe.

Table 1. AE Severity Grading

AE Relationship to Study Treatment

The relationship of an AE to the study treatment should be assessed using the following the guidelines in Table 2.

Relationship to Drug	Comment	
Definitely	Previously known side effect of treatment; or an event that follows a reasonable temporal sequence from administration of the treatment; that follows a known or expected response pattern to the suspected treatment; that is confirmed by stopping or reducing the treatment; and that is not explained by any other reasonable hypothesis.	
Probably	An event that follows a reasonable temporal sequence from administration of the treatment; that follows a known or expected response pattern to the suspected treatment; that is confirmed by stopping or reducing the treatment; and that is unlikely to be explained by the known characteristics of the subject's clinical state or by other interventions.	
Possibly	An event that follows a reasonable temporal sequence from administration of the treatment; that follows a known or expected response pattern to that suspected treatment; but that could readily have been produced by a number of other factors.	
Unrelated	An event that can be determined with certainty to have no relationship to the study treatment.	

Table 2. AE Relationship to Study Drug

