incidence of painful swallowing after TEE insertion is 0.1%,²⁶ and the risk of discomfort after ECD placement is expected to be even lower. To minimize the risk of discomfort, ECDs will be well-lubricated and only placed by study doctors experienced in the placement of OG tubes and TEE probes (attending liver transplant anesthesiologists). While placement of the ECD could theoretically cause gastrointestinal bleeding from varices, placement of larger probes for TEE is generally considered safe during LTx and routinely performed by 86% of liver transplant anesthesiologists in the US.^{27,28}

Mild intraoperative hypothermia has few potential risks.²⁹ Currently 23% of patients experience temperatures < 35 °C during LTx at UCSF (data not shown), although not in a precisely controlled fashion as proposed in this trial. Hypothermia can exacerbate coagulopathy and increase transfusion requirements, but this is mainly described at temperatures below our proposed range of 34-35 °C. Increased bleeding was NOT seen in a large randomized controlled trial (RCT) of cooling to 33 °C in intracranial aneurysm surgery.³⁰ Nevertheless, to mitigate the risk of coagulopathy from hypothermia, the attending liver transplant surgeon will be asked to rate the degree of coagulopathy on a qualitative scale at various points in the operation (see below). If mild hypothermia is felt to be contributing to a coagulopathy that is unsafe for the patient, either the attending surgeon or anesthesiologist may request abortion of the hypothermia protocol at any point in the operation and rewarming of the patient will be initiated. Cardiovascular instability was not observed in a secondary analysis of the aneurysm trial mentioned above³¹ or in the trial of brain-dead kidney donors.¹⁴ Hypothermia has been reported to increase surgical site infections and bacteremia,^{29,30} but we are confident that this can be prevented by active warming prior to case end and the current antibiotic protocols for LTx.

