- The change in urine NGAL level from baseline to 2 hours after reperfusion of the portal vein will be summarized by median and interquartile range by arm and compared by two-sample t-tests, or Mann-Whitney U tests if the normality assumption does not hold.

Safety and tolerability data will be summarized by treatment group.

Adverse event rates will be coded by body system and MedDra classification term. Adverse events will be tabulated by treatment group and will include the number of patients for whom the event occurred, the rate of occurrence, and the severity and relationship to study treatment.

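### Table 2 can show more definitely related bleeding and infection under hypothermia even when the two arms have equal event rates

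*Combined protocol and SAP*

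**What the plan says.** Section 11.1 asks that each adverse event be graded for relationship using Table 2, whose column header and caption speak of a drug although the trial has none.

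- *Definitely* has two routes. The first is simply being on record as a side effect. The second is a set of joint conditions: "Previously known side effect of treatment; or an event that follows a reasonable temporal sequence from administration of the treatment", and so on, including a stop-or-reduce test.
- *Probably* repeats that test: "that is confirmed by stopping or reducing the treatment; and that is unlikely to be explained" by the subject's clinical state or other interventions.
- *Possibly* has no such test. It needs a plausible time sequence and a known or expected response pattern, "but that could readily have been produced by a number of other factors".
- *Unrelated* is "An event that can be determined with certainty to have no relationship to the study treatment".

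Section 2.1 names effects of hypothermia: "Hypothermia can exacerbate coagulopathy and increase transfusion requirements" and "Hypothermia has been reported to increase surgical site infections and bacteremia". It qualifies both. Section 15.4 tabulates adverse events by arm, giving patient counts and rates together with "the severity and relationship to study treatment". Section 8.2 says that the intervention is finished in the operating room and that the anesthesiologist investigators know the arm.

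**The concern.** The scale suits a drug given over time, which can be stopped to see whether the event resolves. Here the treatment lasts some hours under anesthesia. An infection or swallowing complaint found on the ward cannot be confirmed by withdrawing something that has already ended.

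The opening clause of *Definitely* raises a separate problem. It attaches the highest grade to a type of event, not to evidence about the individual case. If bleeding and infection count as effects of hypothermia and no effects of normothermia are on record, the same event can receive different grades in the two arms. Section 11.1 has the investigator record relationship, and Section 8.2 blinds only the staff who adjudicate AKI, so nothing in the procedure corrects for this. At stake is how a reader would interpret the relatedness column for the two risks that Section 2.1 itself raises.

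**Working it through.** The plan states no figure on this point, so the check is mainly a reading of the definitions.

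**Step 1: the conditions side by side (Table 2).**

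| Grade | On record as a side effect | Time sequence | Known or expected pattern | Stop-or-reduce confirmation | Other causes |
|---|---|---|---|---|---|
| Definitely, route A | sufficient alone | – | – | – | – |
| Definitely, route B | – | required | required | required | no other reasonable explanation |
| Probably | – | required | required | required | unlikely |
| Possibly | – | required | required | – | readily possible |
| Unrelated | – | – | – | – | certainty of no relationship |

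**Step 2: apply them to the events listed in Section 5.3E.**

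- *Surgical site infection, cooled arm.* Route A is open if the effect named in Section 2.1 is taken as known. If it is not, route B and *Probably* are closed because the treatment is over, and *Possibly* is the highest grade left.
- *Surgical site infection, control arm.* Route A is closed because no side effect of normothermia is given. The response-pattern condition fails for the same reason, so even *Possibly* is not clearly available, and *Unrelated* needs certainty. Read strictly, the event fits no grade.
- *Bleeding with coagulopathy during surgery.* Route A separates the arms in the same way. Here the stop-or-reduce test can in principle be observed, because Section 2.1 allows the protocol to be aborted and the patient rewarmed.
- *Throat discomfort, difficulty swallowing.* Section 2.1 names these as possible ECD effects, and Section 4.1 places an ECD in every subject. Route A is open in both arms, so grading is alike.

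**Step 3: size under stated assumptions.** Let *n* be patients per arm, *r* an equal event rate in both arms, and *h* the share of events that are hypothermia-type, with the rest ECD-type. Assume that every event is graded by route A wherever it is open.

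- *Definitely* count, cooled arm = n × r
- *Definitely* count, control arm = n × r × (1 − h)
- Artificial gap = r × h

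Inputs: n = 230 / 2 = 115 (Section 8.1, 1:1 allocation). The rates are illustrative. 5% and 10% are borrowed from Section 15.5.2, where they are the upper bound on the expected combined incidence of grade 3–4 events and the stopping threshold. The documents do not give *h*.

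At r = 5% there are 115 × 0.05 = 5.75 events per arm:

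| h | Cooled | Control | Gap (percentage points) |
|---|---|---|---|
| 0 | 5.75 | 5.75 | 0 |
| 0.25 | 5.75 | 4.31 | 1.25 |
| 0.5 | 5.75 | 2.88 | 2.5 |
| 0.75 | 5.75 | 1.44 | 3.75 |
| 1 | 5.75 | 0 | 5 |

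At r = 10% there are 11.5 events per arm and the gap runs from 0 to 10 points. Rounded to 12 of 115 in each arm, Fisher's exact test on all events gives p = 1.0. If all 12 are hypothermia-type, the *Definitely* counts are 12 and 0, with p = 0.0004. The plan specifies no test of this column; the p-value only shows how persuasive an artifact could look.

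**The case against.** The strongest reply is that nothing the trial decides depends on Table 2. Section 15.4 tabulates counts and rates by arm whatever the relationship. Infections, transfusion, blood loss and surgeon-rated coagulopathy are safety evaluations in their own right (Section 5.3). SAEs are documented whether or not related (Section 11.2.1), and the stopping rule uses severity only (Section 15.5.2). At equal rates, the same table would show equal totals. All of this stands and confines the harm to the relatedness column.

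Section 2.1 also softens the premise. It places the coagulopathy risk mainly below 34–35 °C, cites a trial at 33 °C without increased bleeding, and expects infection to be preventable. An assessor might therefore not treat either as a known effect of this treatment. Section 11.1 calls Table 2 guidelines. And the imbalance arises only if treatment, which Table 2 leaves undefined, is read as the assigned temperature. These points make the distortion possible rather than certain. They also show that the table leaves the choice to an assessor who may know the arm.

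A reader might go further and infer that ECD throat or esophageal injuries are understated. The documents largely do not support that: Section 2.1 already names sore throat and difficulty swallowing, so these can be graded *Definitely* in both arms. Only a delayed device injury not regarded as known would be limited to *Possibly*, and equally so in each arm.

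**Conclusion.** The point holds in limited form. Route A carries no causal test, and the stop-or-reduce condition cannot be met for events that begin after treatment has ended. For hypothermia-type events, equal rates can give unequal *Definitely* counts by arm, with a gap between zero and the full event rate (0 to 5 points at an assumed 5%, 0 to 10 at an assumed 10%). This rests on bleeding and infection being taken as known effects, on treatment being read as the temperature arm, and on an event mix that the documents do not state.

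Two stronger readings are tempting and unsupported. One is that Table 2 demands stop-or-reduce confirmation for every related grade; *Possibly* does not. The other is that the safety tables as a whole are lopsided or the safety conclusions corrupted; ECD-type events are graded alike, and all-event rates, SAE reporting and the stopping rule do not use relatedness. The importance is low, but the correction is easy.

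**What to change.** In Table 2:

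1. Delete the opening clause of *Definitely*, so that being on record as a side effect is no longer sufficient.
2. Waive the stop-or-reduce condition for events that begin after the temperature protocol has ended or the ECD has been removed.
3. Define treatment, and grade relationship to the temperature protocol and to the ECD separately, with the same criteria in both arms. The first change alone would not be enough, because the response-pattern condition stays in all three related grades and would still separate the arms.

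In Section 15.4, add one sentence: between-arm safety conclusions rest on the all-event rates already tabulated, and relatedness is descriptive only.

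The cost is a few lines of wording. The downside is that adverse events already recorded need re-grading for relationship, by assessors who may know the arm. The Section 15.4 sentence limits what that re-grading can affect.

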11.2 Serious Adverse Experiences (SAE)

An SAE is defined as any AE occurring at any dose that results in any of the following outcomes:

- death
- a life-threatening adverse experience
- inpatient hospitalization or prolongation of existing hospitalization
- a persistent or significant disability/incapacity

• a congenital anomaly/birth defect

Other important medical events may also be considered an SAE when, based on appropriate medical judgment, they jeopardize the subject or require intervention to prevent one of the outcomes listed.

